Section 1.3 Schedule of Activities (SoA): Open Label Treatment	Repositioned/added table footnote superscripts (number 13) and updated text for footnotes 7, 8 and 13.	Clarification for Investigators.
Section 3 Objectives, Endpoints and Estimands	Updated the secondary endpoint 'Histological severity as determined by the Geboes Score at Week 10' to 'Histological severity as determined by the Geboes Histological Index at Week 10'.	Correction to align mismatched text with Section 1.1 (Synopsis).
Section 4.1.2 Open Label Treatment for	Added 'clinical response is calculated centrally in eCRF' and removed the	Clarification for Investigators.

Section # and Name	Description of Change	Brief Rationale
Non-Responders	ambiguity for non-responders at Week 22: for these participants there are no remaining scheduled visits other than the Follow-up Visit.	
Section 4.3.3. Open Label Treatment	Deleted a redundant sentence, as not relevant to the 'Dose Justification' section.	Clarification for Investigators.
Section 4.4 End of Study Definition	
"Participants who withdraw from the study early should be encouraged to complete all visits for that specific phase as set out in the SoA (Section 1.3); however, if this is not possible at a minimum participants will be asked to complete all assessments at both the Early Withdrawal visit and a Follow-Up visit approximately 16 weeks after the last dose (Section 7.2) to ensure participant monitoring following drug wash out."
 
 Added 'for that specific phase'. Changed 'until drug washout is achieved' to 'following drug washout'. 	Clarification for Investigators.
Section 6.2 Intervention Administration	Updated Table 1 and Table 2 to Increase the post dose monitoring period, for the first SC dose, from 30 mins to 2 hours.	Response to a request from a Health Authority, following Protocol Amendment 3 review.
	Updated Table 1 and Table 2 to include the flush time for the 3rd and 4th IV doses.	Clarification for Investigators: to be consistent with the 1st and 2nd IV dosing duration, which includes the flush time.
Section 6.3 Preparation/Handling/ Storage/Accountability	Deleted 'from GSK' to clarify that a Material Safety Data Sheet (MSDS)/ equivalent is 'available upon request.'	Clarification for Investigators.

1. PROTOCOL SUMMARY

1.1. Synopsis

Protocol Title: A multicentre randomized, double-blind, placebo-controlled Phase 2 study to evaluate the safety, tolerability, efficacy, dose-response, pharmacokinetics and pharmacodynamics of repeat dosing of an anti-LAG3 cell depleting monoclonal antibody (GSK2831781) in patients with active ulcerative colitis.

Short Title: Safety, tolerability, efficacy and dose-response of GSK2831781 in ulcerative colitis.

Rationale:

T cells are integral to the pathogenesis of ulcerative colitis (UC), and clinical experience with anti-integrin monoclonal antibodies has established the principle of T cell-targeted therapies in the disease. Lymphocyte Activation Gene-3 (LAG3) is expressed on recently activated T cells, and LAG3⁺ T cells are present in only low numbers in the circulation and healthy tissues. They are, however, increased in the colon in active UC, where their numbers correlate with disease activity [Slevin, 2018]. GSK2831781 causes targeted depletion of LAG3⁺ T cells and has shown preliminary evidence of clinical efficacy in plaque psoriasis (another T cell-mediated disease). It is therefore hypothesized that GSK2831781 will selectively deplete activated mucosal T cells in UC, but with relative sparing of resting T cells.

Objectives and Endpoints:

Objectives	Endpoints
Primary	

 To evaluate the safety and tolerability of repeat doses of GSK2831781 during the Double-Blind Induction Phase. To characterise the efficacy dose-response of GSK2831781 during the Double-Blind Induction Phase. 	
 Incidence of adverse events and serious adverse events during the Double-Blind Induction Phase. Incidence of findings of potential clinical importance¹ during the Double-Blind Induction Phase for: 
 Vital signs Clinical laboratory values (haematology, clinical chemistry and urinalysis). QTc. Change from baseline in Complete 4-domain Mayo score² at Week 10.

Objectives	Endpoints
Secondary	

 To evaluate the safety and tolerability of repeat doses of GSK2831781 during the Double-Blind Extended Treatment Phase. 	
 Incidence of adverse events and serious adverse events in the Double-Blind Extended Treatment Phase. Incidence of findings of potential clinical importance during the Double-Blind Extended Treatment Phase for: 
 Vital signs Clinical laboratory values (haematology, clinical chemistry and urinalysis). QTc.

 To investigate the effect of repeat doses of GSK2831781 on clinical efficacy including endoscopic mucosal healing during the Double-Blind Induction Phase. 	
 Adapted Mayo endoscopic score of 0 or 1 at Week 10. Adapted Mayo clinical remission³ at Week 10. Adapted Mayo clinical response³ at Week 10. Symptomatic remission⁴ over time. Change from baseline in Partial Mayo score over time. Change from baseline in Adapted Mayo endoscopic score and Ulcerative Colitis Endoscopic Index of Severity (UCEIS) at Week 10.

 To investigate the effect of repeat doses of GSK2831781 on UC histologic disease activity during the Double-Blind Induction Phase. 	
 Histological severity as determined by the Robarts Histopathology Index at Week 10. Histological severity as determined by the Nancy Histological Index at Week 10. Histological severity as determined by the Geboes Histological Index at Week 10.

 To investigate the effect of repeat doses of GSK2831781 on biomarkers of UC disease activity during the Double-Blind Induction Phase. 	
 Change from baseline in serum C-reactive protein over time. Change from baseline in faecal calprotectin over time.

 To investigate the pharmacokinetics of GSK2831781 following subcutaneous dosing. 	
 GSK2831781 PK parameters: AUC(0-tau), Cmax, tmax.

Objectives	Endpoints

 To investigate the immunogenicity of repeat doses of GSK2831781 during the Double-Blind Induction Phase. 	
 Incidence of anti-drug antibodies at each visit.
Safety	

 To evaluate the safety and tolerability of repeat doses of GSK2831781 in all trial phases. 	
 Adverse events, vital signs, clinical laboratory values (haematology, clinical chemistry, and urinalysis), 12-lead ECG.

 To investigate the immunogenicity of repeat doses of GSK2831781 in all trial phases. 	
 Incidence of anti-drug antibodies at each visit.

Footnotes:

- 1 Potential clinical importance is defined in the RAP for each relevant safety endpoint.
- 2 The Complete 4-domain Mayo score is used for the primary endpoint due to its wider dynamic range for assessment of dose-response compared to the Adapted Mayo score used for secondary and exploratory endpoints.
- 3 Clinical response and remission for the various iterations of the Mayo score are defined in [Appendix 7](#), Section 10.7.
- 4 Symptomatic remission is defined as a rectal bleeding subscore of 0, and a stool frequency subscore of ≤ 1 , with no worsening from baseline.

Overall Design:

This is a Phase 2, multicentre, randomized, double-blind, parallel group, placebo-controlled study to investigate safety, tolerability, efficacy and dose-response of GSK2831781 in participants with moderate to severe active UC as defined by a 4-domain (Complete) Mayo score of 6-12. The study will consist of five arms: GSK2831781 at 450 mg, 300 mg, 150 mg and 45 mg and a placebo group and will investigate the Induction (up to Week 10), and maintenance with an Extended Treatment Phase (Weeks 10-30), of the achievement and maintenance of clinical response, remission and mucosal healing.

In addition, Non-Responders identified following the Week 10 assessment will be moved to open label treatment consisting of Induction (Weeks 12 to 22), an Extended Treatment Phase (Weeks 22 to 52), and a Follow-Up to Week 54.

Disclosure Statement: This is a parallel group treatment study with five arms that is participant, Investigator and sponsor blinded.

Number of Participants:

Approximately 242 participants will be randomly assigned to study intervention under the assumption that a proportion will not receive all planned doses up to Week 10 and/or have an incomplete Week 10 Complete 4-domain Mayo score assessment. If the attrition rate is higher than planned for (e.g., 15% or more) then additional participants, up to a maximum of 320, may be recruited.

[figure not shown]
Intervention Groups and Duration:

Total duration for participants who respond to GSK2831781 will be approximately 47 weeks (see Section 1.2). The study consists of a 5-week screening window, 10-week Induction Phase (IP), 20-week Extended Treatment Phase (ETP), and a 12-week Follow-Up Phase. Non-Responders allocated to Open Label Treatment (GSK2831781 450 mg) who subsequently respond to treatment may spend up to 59 weeks in total on study. Intervention groups are shown in the schema below, Section 1.2.

Data Review Committee (DRC):

A DRC will be utilised in this study to review the interim analyses data in an unblinded manner. The DRC will be comprised of a predefined subset of project team members, senior GSK stakeholders and experts external to the project team to ensure that persons with the appropriate expertise and knowledge conduct and interpret interim reviews of data. No study personnel with direct contact with sites or site staff will be involved in the DRC (see Appendix 1, Section 10.1.5).

1.2. Schema

*Randomisation will initially be 2:1 to GSK2831781 450 mg or Placebo. When an appropriate number of participants have been randomised in these two arms for the interim analysis (Interim Analysis 3, see Section 9.5), randomisation to all dose regimens (GSK2831781 450 mg, 300 mg 150 mg, 45 mg or placebo) will be opened at a ratio of 2:3:3:3:2.. Dosing during the Double-Blind Induction Phase will be undertaken at Weeks 0 (Day 1), 2, 6 and 10. Responders at Week 10 (where Responder status is determined by a pre-specified algorithm in the eCRF) will continue into the Double-Blind ETP.

Participants originally randomised to GSK2831781 IV treatment arms (Induction) will receive subcutaneous doses of 300 mg GSK2831781 every 4 weeks at Weeks 14, 18, 22, and 26. Participants originally on placebo treatment arm, who attained response, will continue to receive blinded placebo through SC dosing at Weeks 14, 18, 22 and 26. The Double-Blind ETP ends at Week 30, with Follow-Up until Week 42 (16 weeks after the last dose).

[†]The open label patient journey is described fully in Section 4.1.2 and [Figure 3](#). The Open Label ETP, for Non-Responders at Week 10, will constitute a full 10 weeks of induction dosing according to the same dosing schedule as GSK2831781 450 mg (IV doses at Weeks 12, 14, 18 and 22). The Open Label Induction Phase (OLIP) will start at Week 12 to allow turnaround of centrally determined responder status. Response following OLIP will be assessed at Week 22 in the Open Label ETP, and Responders will continue with doses of 300 mg GSK2831781 subcutaneously every 4 weeks from Week 26 to 38. Participants will then undertake a Follow-Up period of 12 weeks from Week 42 to Week 54. Participants in the Open Label ETP who are Non-Responders at Week 22 will discontinue study treatment and be managed according to physician standard of care but are still required to attend a Follow-Up visit approximately 16 weeks from the last dose event.

1.3. Schedule of Activities (SoA):

Double-Blind Treatment SoA

WEEK	Screening		Induction Phase					Extended Treatment Phase					Follow-Up ²⁰	Early Withdrawal Visit ^{21, 26}		
	Pre-dose	Post-dose	2	4 ²⁶	6	10	12 ¹⁹	14	18 ²⁶	22 ²⁶	26 ²⁶	30	42 ²⁶			
DAY	-35 to -7 ²³	-14 to -7 ¹⁴	Day 1		15	29	43	71	85	99	127	155	183	211	295	
Window (days)					±2	±3	±3	±3	±5	±3	±3	±3	±3	±3	±7	
Study Population																
Informed Consent	X															
Inclusion/Exclusion Criteria	X															
Demography	X															
Weight	X							X		X			X	X	X	
History ¹ (Medical/Disease/IBD Therapy)	X															
Extra-Intestinal Manifestations History	X															
Smoking status	X						X						X	X	X	
Efficacy																
Determination of 'Normal' stool count for Mayo Score	X															
Endoscopy with Biopsy ²		X						X					X		X ²²	
Mayo (Complete or Partial)	P	C	P	P	P	P	C		P	P	C	P	C	P	C ²² /P	
Steroid Taper								X								
Extra-Intestinal Manifestations Activity			X				X					X	X	X		
Safety Assessments																
Vital Signs	X		X	X ¹⁶	X ¹⁶	X	X	X		X ¹⁶	X ¹⁶	X	X	X	X	
12-lead ECG ³	X		X	X ¹⁶				X			X			X	X	
Full/Brief Physical	F		B	B	B	B	B		B	B	B	B	B	F	F	
Concomitant Medications	X		<----->													
AEs / SAEs ⁴			<----->													
Haematology ⁵	X		X		X	X	X	X		X	X	X	X	X	X	
Clinical chemistry (incl. CRP) ⁵	X		X		X	X	X	X		X	X	X	X	X	X	
Pregnancy Test (WOCBP) ^{5, 6}	X		X		X	X	X	X		X	X	X	X	X	X	

WEEK	Screening		Induction Phase					Extended Treatment Phase					Follow-Up ²⁰	Early Withdrawal Visit ^{21, 26}		
	Pre-dose	Post-dose	2	4 ²⁶	6	10	12 ¹⁹	14	18 ²⁶	22 ²⁶	26 ²⁶	30	42 ²⁶			
DAY	-35 to -7 ²³	-14 to -7 ¹⁴	Day 1		15	29	43	71	85	99	127	155	183	211	295	
Window (days)					±2	±3	±3	±3	±5	±3	±3	±3	±3	±3	±7	
Urinalysis ⁵	X		X		X	X	X	X	X	X	X	X	X	X	X	X
TB – QuantiFERON ± PPD ⁷	X															
Serology (HIV, HBV, HCV, CMV, EBV and VZV)	X															
Clostridium difficile toxin	X															
FSH & oestradiol (if appropriate) ⁸	X															
Dosing and PK/PD																
Randomization			X ²⁷													
IMP administration ⁹			IV		IV		IV	IV	SC	SC	SC	SC				
PK ^{10, 11}			X	X ¹⁷	X		X ¹⁸	X	X	X	X	X	X	X	X	X
sLAG3 ^{10, 11}			X	X ¹⁷	X		X ¹⁸	X	X	X	X	X	X	X	X	X
Blood proteomic signature ⁵			X		X			X								
Blood transcriptomic signature ⁵			X													
LAG3 Cell Depletion (by Flow Cytometry) ^{5, 12}			X		X		X						X	X ²⁸	X ²⁸	
Immunogenicity			X		X	X		X	X	X		X	X	X	X	X
4β-hydroxycholesterol (4βHC) ⁵			X				X									
Faecal Calprotectin ²⁴			X		X		X	X		X		X	X	X	X	X
Serum Trypsase ⁵			X			X	X			X		X	X	X	X	X
Patient Reported Outcomes																
IBDQ, FACIT-Fatigue and SF-36 ¹³			X				X	X				X	X	X	X	X
Bowel symptom eDiary			<----->													
PGIC & PGIS ¹³			X ¹⁵				X					X	X	X	X	X
Exit Interview													X ²⁵		X ²⁵	
Other																
PGx Sample			X													

Footnotes:

- 1 See SRM for requirements for data collection.
- 2 Endoscopy should be flexible sigmoidoscopy. However, colonoscopy can be performed at screening if required for assessment of dysplasia risk (see Section 5.1), and at any timepoint if clinically indicated.
- 3 ECG in triplicate at screening and single at all other time points. See Section 8.6.3, Electrocardiograms for further detail.
- 4 Collection of SAEs starts from screening whilst collection of AEs will commence from Day 1.
- 5 Unless specified otherwise, all samples will be taken prior to administration of study treatment.
- 6 Negative test required during screening and immediately prior to the first dose of study treatment. A serum pregnancy test is required at screening, after which a highly sensitive urine pregnancy test is adequate. If a urine test cannot be confirmed as negative, a serum pregnancy test is required.
- 7 A PPD test maybe performed following two indeterminate Quantiferon tests to determine TB status, see Section 5.2.
- 8 To confirm postmenopausal status, serum FSH and oestradiol testing will be performed for all postmenopausal females at the screening visit.
- 9 See Section 6.2 for details of dosing duration and monitoring period.
- 10 Unless stated, samples taken on a day of dosing must be pre-dose sample (up to 2 hr before the next dose).
- 11 Additional sampling will be required in a subset of participants to characterise SC pharmacokinetics. See Section 8.3, for schedule.
- 12 LAG3 depletion will only be undertaken in sites where shipping to central lab can be achieved in the required timeframe, see Section 8.4, and SRM.
- 13 IBDQ, FACIT-Fatigue, SF-36, PGIC and PGIS are to be performed before any other assessments on visit days.
- 14 A 7-day window enables turnaround of centrally read endoscopy score for inclusion to arrange Day 1 visit; however, endoscopy can be performed up to Day -3 if all other criteria for study eligibility have been met by this time and Robarts have agreed rapid turnaround of central endoscopy read.
- 15 PGIC not to be done on Day 1.
- 16 Vital signs to be taken every 30 minutes (\pm 5 minutes) until completion of post dose monitoring period. A single ECG be taken within 4 hours of completion of dose administration. For participants who have discontinued treatment but remain on study, post-dose monitoring does not apply.
- 17 Samples to be taken immediately after end of IV infusion (preferably within 15 minutes).
- 18 Samples to be taken up to 2 hr before the next dose, and one sample immediately after end of IV infusion (within 15 minutes).
- 19 Week 12 visit scheduled to enable recall of Non-Responders to move to Open Label dosing at Week 12, see Open Label Treatment SoA below. Telephone call can be used to ensure Responders initiate steroid taper and cancel scheduled visit for Responders next due to undertake dosing at Week 14.
- 20 In case of Early treatment discontinuation, or study withdrawal, the investigator should undertake a Follow-Up visit approximately 16 weeks after the last dose event to allow safety monitoring following drug washout.
- 21 Participants who discontinue study treatment are encouraged to complete remaining scheduled visits for the treatment phase they are in. However, an Early withdrawal visit is only required for participants who prematurely discontinue study treatment and do not agree to complete the remaining scheduled visits for that phase.
- 22 Complete 4-domain Mayo Score (including Endoscopy) to be performed if withdrawal from study treatment occurs after Week 4 but prior to Week 10 (all participants) or between Week 18 and Week 30 for Responders. The endoscopy is to be performed either at the Early Withdrawal Visit (for participants who do not wish to complete remaining scheduled visits), or at Week 10 or Week 30 (for participants that agree to complete remaining scheduled visits after withdrawing from treatment).
- 23 The window for Screening Visit 1 can be extended to Day -45 where indeterminate test results are returned for assays requiring long central laboratory turnaround times (e.g., QuantiFERON and *C. difficile*). However, if haematology, clinical chemistry and (if applicable) serum pregnancy tests have been

performed outside of the Day -35 window they must be repeated and recorded as an unscheduled visit in the eCRF to confirm eligibility, even if performed at Screening Visit 2.

- 24 Faecal Calprotectin sample may be taken up to 48 hours prior to scheduled visit.
- 25 Exit interview, if applicable, to be undertaken either at Early Withdrawal or Follow-Up.
- 26 Home health care / telemedicine visits may be permitted where applicable country and local regulations and infrastructure allow.
- 27 Randomisation may be performed on Day -1. Randomisation may only proceed when all information pertaining to patient eligibility has been confirmed, including eCRF Mayo score eligibility calculation.
- 28 Samples only to be taken for participants that achieved a responder status at Week 10 and subsequently withdraw from treatment.

- Safety, pharmacokinetic, pharmacodynamic/biomarker or other assessments may be altered during the study based on newly available data (e.g., to obtain data closer to the time of peak plasma concentrations) to ensure appropriate monitoring.
- Any changes in the timing or addition of time points for any planned study assessments as the result of emerging pharmacokinetic/pharmacodynamic data from this study must be documented and approved by the relevant study team member and then archived in the sponsor and site study files, but will not constitute a protocol amendment. The Competent Authority (CA) and ethics committee (EC) will be informed of any safety issues that constitute a substantial amendment and require alteration of the safety monitoring scheme or amendment of the informed consent form (ICF). The changes will be approved by the CA and the EC before implementation.
- For details on home healthcare and telemedicine approaches, please refer to [Appendix 10](#).

Open Label Treatment SoA

	Open Label Induction Phase				Open Label Extended Treatment Phase						Open Label Follow up ⁷	Open Label Early Withdrawal Visit ^{8, 12}	
	WEEK	12	14	18	22	24	26	30 ¹²	34 ¹²	38 ¹²	42 ¹²		
DAY	85	99	127	155	169	183	211	239	267	295	379		
Window (days)	±5	±3	±3	±3	±3	±3	±3	±3	±3	±3	±7		
Endoscopy with Biopsy				X									X
Mayo (Complete or Partial)	P	P	P	C			P		P	P	P		C ¹³ /P
Extra-Intestinal Manifestations Activity				X						X	X		X ¹³
Steroid Taper					X								
Weight				X						X			
Safety Assessments													
Vital Signs	X ⁵	X ⁵	X	X		X ⁵	X ⁵	X	X	X	X		X
12-lead ECG	X ⁹			X								X	X
Full/Brief Physical	B	B	B	B		B	B	B	B	B	F		F
Concomitant Medications	<----->												
AEs / SAEs	<----->												
Haematology ¹	X	X	X	X		X	X	X	X	X	X		X
Clinical chemistry (incl. CRP) ¹	X	X	X	X		X	X	X	X	X			X
Pregnancy Test (WOCBP) ^{1, 2}		X	X	X		X	X	X	X	X			X
Urinalysis ¹	X	X	X	X		X	X	X	X	X			X
Dosing and PK/PD													
IMP administration ³	IV	IV	IV	IV		SC	SC	SC	SC				
PK ¹	X ⁶			X ⁶						X	X		X
sLAG3 ¹	X ⁶			X ⁶						X	X		X
Immunogenicity ¹	X	X		X			X		X	X	X		X
Faecal Calprotectin ¹⁰	X		X	X					X	X	X		X
Patient Reported Outcomes													
IBDQ, FACIT-Fatigue and SF-36 ⁴			X	X					X	X	X		X
Bowel symptom eDiary	<----->												
PGIC & PGIS ⁴				X						X	X		X
Exit Interview											X ¹¹		X ¹¹

Footnotes:

- 1 Unless specified otherwise, all samples will be taken prior to administration of study treatment.
- 2 A highly sensitive urine pregnancy test is adequate. If a urine test cannot be confirmed as negative, a serum pregnancy test is required.
- 3 See Section 6.2, for details of dosing durations and monitoring periods.
- 4 IBDQ, FACIT-Fatigue, SF-36, PGIC and PGIS are to be performed before any other assessments on visit days.
- 5 Vital signs to be taken every 30 minutes (± 5 minutes) until completion of post dose monitoring period. For participants who have discontinued treatment but remain on study, post-dose monitoring does not apply.
- 6 Additional PK sample immediately after end of IV infusion (preferably within 15 minutes of end of IV infusion).
- 7 In case of Early treatment discontinuation, or study withdrawal, the investigator should undertake a Follow-Up visit approximately 16 weeks after the last dose event to allow safety monitoring following drug washout.
- 8 Participants who discontinue study treatment are encouraged to complete remaining scheduled visits for the treatment phase they are in. However, an Early withdrawal visit is only required for participants who prematurely discontinue study treatment and do not agree to complete the remaining scheduled visits for that phase.
- 9 A single ECG to be taken any time within post-dose monitoring period
- 10 Faecal Calprotectin sample may be taken up to 48 hours prior to scheduled visit.
- 11 Exit interview, if applicable, to be undertaken either at Early Withdrawal or Follow-Up.
- 12 Home health care / telemedicine visits may be permitted where applicable country and local regulations and infrastructure allow.
- 13 Complete 4-domain Mayo Score (including Endoscopy) to be performed if withdrawal from study treatment occurs after Week 16 but prior to Week 22 (all participants). The endoscopy is to be performed either at the Early Withdrawal Visit (for participants who do not wish to complete remaining scheduled visits), or at Week 22 (for participants that agree to complete remaining scheduled visits after withdrawing from treatment).

- Safety, pharmacokinetic, pharmacodynamic/biomarker and/or other assessments may be altered during the study based on newly available data (e.g. to obtain data closer to the time of peak plasma concentrations) to ensure appropriate monitoring.
- Any changes in the timing or addition of time points for any planned study assessments as the result of emerging pharmacokinetic/pharmacodynamic data from this study must be documented and approved by the relevant study team member and then archived in the sponsor and site study files, but will not constitute a protocol amendment. The Competent Authority (CA) and ethics committee (EC) will be informed of any safety issues that constitute a substantial amendment and require alteration of the safety monitoring scheme or amendment of the informed consent form (ICF). The changes will be approved by the CA and the EC before implementation.
- For details on home healthcare and telemedicine approaches, please refer to [Appendix 10](#).

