	
Clinical:
 
WOCBP were included in the psoriasis cohorts of study 200630, with appropriate pregnancy testing and contraceptive requirements. No pregnancies have been observed.
 
The IMP level of mAb in human semen is expected to be too low to be of concern.
	
contraception throughout the study until after the Follow-Up visit.
 
Pregnancy testing will be performed at screening and prior to the first dose, at least monthly during the dosing period, and at regular intervals until Follow-Up, as documented in the clinical protocol.
 
WOCBP who are partners of male subjects in the study will not be required to be protected from seminal fluid exposure or need to use a condom plus highly effective method of contraception.

Study Procedures		
Endoscopy with biopsy	
Whilst endoscopic examination of the gut is generally well tolerated, potential risks of the procedure include discomfort, bleeding or perforation (1/5000 for sigmoidoscopy and 1/3000 for colonoscopy).
	
Sigmoidoscopy rather than colonoscopy (unless a colonoscopy is clinically indicated, for example for malignancy/dysplasia screening at baseline) will be used to reduce risk of endoscopy-related complications. Endoscopy will be performed by experienced and trained staff only.
 
Participants will be informed of expected post-procedure bleeding and will be instructed to contact the clinical site should they experience any adverse events after the procedure.

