Participants will be followed for 16 weeks after the last administration of GSK2831781. Due to the non-linear nature of the PK and limited number of observations in the final phase, the terminal half-life could not be determined in the FTIH study 200630. However, the data from this study show that after dosing at 5 mg/kg IV (470 mg on average), the mean plasma concentration of GSK2831781 at Day 85 (i.e. 12 weeks after dosing) had dropped to 0.5 µg/mL, from a mean Cmax of 162 µg/mL, and in 2 out of 6 participants the concentration had dropped below the limit of quantification (10 ng/mL). At Day 121 (i.e. 17 weeks after dosing; next time point for PK), the concentrations in all participants who had received 5 mg/kg had dropped below the limit of quantification. Since only very limited accumulation is expected for monoclonal antibodies in general and, based on population PK modelling of the data from study 200630, a wash out period of 16 weeks after the last administration has been selected as a sufficient time for washout and determination of repletion of LAG3⁺ cells.

A key feature of the study is that there will be a number of interim analyses that may be performed, which will include the assessment of PK and an assessment of futility (see Section 9.5 for further details).

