4.3.3. Open Label Treatment

All participants who did not respond during the double-blind Induction Phase will receive 450 mg IV at Weeks 12, 14, 18 and 22 (Open Label Induction Phase), followed by 300 mg SC every 4 weeks from Week 26-38 (Open Label Extended Treatment Phase). Since only minimal (further) accumulation of GSK2831781 is expected, continuing treatment at 450 mg IV for Non-Responders who might have received this dose during the double-blind Induction Phase as well will result in only limited, if any, increases in exposure.

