10.2. Appendix 2: Clinical Laboratory Tests

The tests detailed in [Table 7](#), will be performed by the central laboratory (Q2).

Local laboratory results are only required:

- In the event that the central laboratory results are not available in time for either study intervention administration and/or response evaluation. If a local sample is required, it is important that the sample for central analysis is obtained at the same time.
- If an emergent result, condition or event warrants further investigation requiring tests not performed by the central laboratory (Q2).

Protocol-specific requirements for inclusion or exclusion of participants are detailed in [Section 5](#) of the protocol.

Additional tests may be performed at any time during the study as determined necessary by the Investigator or required by local regulations.

Pregnancy Testing

- Refer to [Section 5.1](#) Inclusion Criteria for screening pregnancy criteria.
- Pregnancy testing (urine or serum as required by local regulations) should be conducted at intervals specified in the SoA ([Section 1.3](#)) during intervention. In the event of early study withdrawal, pregnancy testing (urine or serum) should be conducted at the end of the relevant systemic exposure plus an additional 30 days.

Table 7 Protocol-Required Safety Laboratory Assessments

Laboratory Assessments	Parameters				
Hematology	Platelet Count	RBC Indices: MCV MCH %Reticulocytes	WBC count with Differential: Neutrophils Lymphocytes Monocytes Eosinophils Basophils		
	RBC Count				
	Hemoglobin				
	Hematocrit				
Clinical Chemistry ¹	BUN	Potassium	Aspartate Aminotransferase (AST)/ Serum Glutamic-Oxaloacetic Transaminase (SGOT)	Total and direct bilirubin	

Laboratory Assessments	Parameters			
	Creatinine	Sodium	Alanine Aminotransferase (ALT)/ Serum Glutamic-Pyruvic Transaminase (SGPT)	Total Protein Albumin
	Glucose (nonfasting)	Calcium	Alkaline phosphatase	C-Reactive Protein
Routine Urinalysis	
 Specific gravity. pH, glucose, protein, blood, ketones, bilirubin, urobilinogen, nitrite, leukocyte esterase by dipstick. Microscopic examination (if blood or protein is abnormal). 			

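### The open-label Follow-Up visit has no clinical chemistry, urinalysis or pregnancy test marked, so Week 22 non-responders have none scheduled after their last 450 mg infusion

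*Protocol*

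**What the plan says.** Protocol Section 1.3 has two schedules, each ending in a Follow-Up visit.

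- **Open-label schedule.** The rows "Clinical chemistry (incl. CRP) ¹", urinalysis and pregnancy test are marked up to Week 42 and at Early Withdrawal. The Follow-Up cell is blank for all three. Haematology, ECG, vital signs, full physical examination, PK, sLAG3 and immunogenicity are marked at Follow-Up. SAP Section 15.2 reproduces the table with the same blanks.
- **Double-blind schedule.** The row "Clinical chemistry (incl. CRP) ⁵", urinalysis and the pregnancy test are all marked at the Week 42 Follow-Up.

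Footnote 7 of the open-label schedule covers participants who stop early: "the investigator should undertake a Follow-Up visit approximately 16 weeks after the last dose event to allow safety monitoring following drug washout". Section 4.2 explains the timing: "a wash out period of 16 weeks after the last administration has been selected as a sufficient time for washout". On pregnancy, the Reproductive Toxicity entry in Section 2.3.1 commits to testing monthly or more often during dosing and then "at regular intervals until Follow-Up, as documented in the clinical protocol".

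Section 4.3.3 states that week 10 non-responders "will receive 450 mg IV at Weeks 12, 14, 18 and 22 (Open Label Induction Phase"). Footnote 1 fixes when the Week 22 samples are drawn: "Unless specified otherwise, all samples will be taken prior to administration of study treatment". Section 4.1.2 then sends participants without a Week 22 response off treatment and requires only a Follow-Up visit about 16 weeks after the last dose. SAP Section 2.3 describes the same path.

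**The concern.** A participant who does everything the protocol asks, but has not responded at Week 22, leaves with no scheduled look at liver enzymes, bilirubin, creatinine, urine or pregnancy status after the final top-dose infusion. Someone who stops prematurely and declines further visits is sent to Early Withdrawal, where all three tests are marked. The compliant participant is therefore scheduled for less.

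Nothing in either document gives a reason for dropping these tests, and the visit exists for safety monitoring. The safety objective in Section 3 covers all trial phases and names clinical chemistry and urinalysis alongside haematology. Section 2.3.1 also lists chemistry among the mitigations for immunogenicity. The open-label Follow-Up collects the antibody sample without the chemistry.

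The cost of the gap is an abnormality that nobody is scheduled to look for at the end of washout, and a pregnancy-testing commitment that the open-label schedule does not deliver.

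**Working it through.** The plan gives no figure to reproduce, so the check compares the tables and counts days.

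**1. Is the blank real?** The SAP copy of the open-label schedule has 12 visit columns: Weeks 12, 14, 18, 22, 24, 26, 30, 34, 38, 42, Follow-Up (54) and Early Withdrawal.

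| Row | Marked at | Follow-Up |
|---|---|---|
| Haematology | 12, 14, 18, 22, 26, 30, 34, 38, 42, EW | yes |
| Chemistry | 12, 14, 18, 22, 26, 30, 34, 38, 42, EW | no |
| Urinalysis | 12, 14, 18, 22, 26, 30, 34, 38, 42, EW | no |
| Pregnancy test | 14, 18, 22, 26, 30, 34, 38, 42, EW | no |
| ECG | 12, 22, EW | yes |

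Chemistry and urinalysis differ from haematology only at Follow-Up. The pregnancy test differs there and at Week 12. In text form the Protocol's own table carries one surplus column, but both cells that could be Follow-Up are blank for all three tests. The two copies agree.

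**2. Is the double-blind Follow-Up marked?** Some rows of the Protocol's double-blind table are shifted by a column in text form. The last two candidate cells (14 and 15) are filled for chemistry, urinalysis and pregnancy test, so Follow-Up is marked on either reading. The SAP copy shows marks at Week 30, Week 42 and Early Withdrawal.

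**3. Days from last dose to each test.** Study day = 7 × week + 1.

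- *Week 22 non-responders.* Last dose: 7 × 22 + 1 = Day 155. Follow-Up: 155 + 16 × 7 = 155 + 112 = Day 267, or Days 260 to 274 with the ±7-day window. The Week 22 samples precede the infusion, so they do not count.
- *Open-label responders.* Last dose: Week 38 = Day 267. Week 42 = Day 295, which is 295 − 267 = 28 days. Week 54 = Day 379, which is 379 − 267 = 112 days.
- *Double-blind responders.* Last dose: Week 26 = Day 183. Week 30 = Day 211, which is 28 days. Week 42 = Day 295, which is 295 − 183 = 112 days.

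| Group | Sets of the three tests after last dose, as planned | With the tests added at Follow-Up |
|---|---|---|
| Week 22 non-responders | 0 | 1 (112 days) |
| Open-label responders | 1 (28 days) | 2 (28 and 112 days) |
| Double-blind responders | 2 (28 and 112 days) | unchanged |

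Haematology at Follow-Up is marked for all three groups already.

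**4. Gap between the last scheduled pregnancy test and Follow-Up.** Week 22 non-responders: 267 − 155 = 112 days. Open-label responders: 379 − 295 = 84 days. Double-blind responders: 0 days.

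**The case against.** The strongest reply is that the gap is small and partly covered elsewhere.

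- **Known abnormalities are followed.** Section 8.6.4 requires clinically significant abnormal results, during the study or within 16 weeks of the last dose, to be repeated until they settle. Appendix 6 adds liver monitoring. This stands for abnormalities already seen by Week 22. It cannot detect one that starts after the infusion, because no chemistry or urine sample is scheduled then.
- **Pregnancy is handled in Appendix 2.** On early study withdrawal, "pregnancy testing (urine or serum) should be conducted at the end of the relevant systemic exposure plus an additional 30 days". SAP Section 2.3 says Week 22 non-responders withdraw from the study after Follow-Up, so the rule may apply to them. Section 4.1.2, however, treats Follow-Up as a required visit on their planned path, so the reading is arguable. It does nothing for chemistry or urinalysis. The commitment in Section 2.3.1 runs until Follow-Up and does not strictly promise a test at that visit.
- **The main risk is covered.** Neutropaenia is the main laboratory concern and haematology is kept. Participants of childbearing potential must use highly effective contraception until Follow-Up, and investigators may add tests. All of this stands and is why the point is minor, although optional tests do not give uniform data.
- **Parity between schedules is not required.** The open-label schedule is lighter in other respects, and SAP Section 2.3 lists rather than summarises post-Week 22 data for Week 22 non-responders. So no summary table for that group changes. The argument rests on the purpose of the visit, not on parity.
- **A sample at about 112 days comes when the drug is expected to have cleared.** True: the added test is an end-of-washout check and no more.

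**Conclusion.** The concern holds as a minor gap in safety monitoring. As written, Week 22 non-responders have 0 scheduled chemistry, urinalysis or pregnancy tests after their final 450 mg infusion. Open-label responders have one set where double-blind responders have two.

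The conclusion concerns what the schedule marks. It assumes that sites follow the schedule, that Week 22 samples are drawn before dosing, and that compliant non-responders do not have an Early Withdrawal visit. The pregnancy part is weaker if Appendix 2 is read as covering this group.

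The documents do not give the expected number of Week 22 non-responders, so the number affected cannot be stated. SAP Section 2.1 records that the sponsor terminated the study on 14 January 2021, which limits the practical effect. No efficacy analysis is touched.

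**What to change.** In the Open Label Treatment schedule of Protocol Section 1.3, mark clinical chemistry, urinalysis and the pregnancy test (for participants of childbearing potential) at Follow-Up, as the double-blind schedule does. Carry the three marks into SAP Section 15.2.

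The visit already takes place and blood is already drawn for haematology. I assume the added burden is about one more blood tube and one urine sample per participant. The documents give no figure for this. Because these would be mandatory tests, the change needs a protocol amendment with ethics approval under Section 10.1.1, and could go in with other changes.

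This adds one check at the end of washout. It does not monitor the interval from Day 155 to about Day 267, which would need an extra visit.
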